184 male partner invitation letters. We will follow couples for 18 months postpartum to assess impact and
185 cost-effectiveness of the intervention on health behaviors and health outcomes. We propose the
186 following specific aims:

187 **Aim 1:** To determine the impact of a couples-focused home-based intervention on our primary outcome
188 of couple HIV testing for pregnant women and their male partners (assessed through proportion
189 reporting couples testing, yield of new HIV+ diagnoses of male partners, and identification of new sero-
190 discordant couples)as compared to HIV self-test kits for couples and standard care.

191 **Aim 2:** To examine the impact of the intervention on HIV prevention behaviors (PrEP and condom
192 use),facility delivery, and postnatal healthcare utilization for all participants; as well as secondary health
193 outcomes of maternal VL suppression, and HIV-free child survival up to 18 months for couples living
194 with HIV; as compared to HIV self-test kits for couples and standard care.

195 **Aim 3:** To compare the cost-effectiveness of the home-based couples intervention to less resource-
196 intensive strategies of standard care and HIV self-test kits for couples. Despite its promise, a home-
197 based intervention may require more resources and it is important to assess whether it offers greater
198 value for money than other strategies, which may cost less but be less impactful.
199

200 **JUSTIFICATION & INNOVATION:**

201 Our study strategy builds upon our team's extensive formative and pilot research and innovates in
202 multiple ways as detailed below: Firstly, it **focuses on couples.** Recent literature and WHO guidance
203 have called for a renewed emphasis on couples to enhance PMTCT and HIV prevention efforts[84-
204 90]and couple-focused interventions have been found to be beneficial in a range of HIV treatment and
205 prevention programs.[91-93]Arecent meta-analysis by Crepaz and colleagues found that couples-based
206 interventions were more effective than individual approaches for both HIV testing and nevirapine
207 uptake.[94]However, there are few couple interventions for pregnant women and male partners in low
208 resource settings.[95].[96]Our proposed study fills this gap by targeting expectant mothers and fathers
209 as a couple. Distinct from existing programs like mothers2mothers[97] our intervention is conducted by

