371 **HIV self-test kits to pregnant women for use together with their male partner:** In order to
372 compare our intervention with a promising, but less resource-intensive, approach for encouraging
373 couple and male partner testing, women in one study group will receive HIVST kits for themselves
374 and their male partner. Trained study staff will provide 4 oral-fluid-based rapid HIV test kits
375 (OraQuickRapid HIV-1/2 Antibody Test, OraSure Technologies – approved for use in Kenya) during
376 pregnancy and up to 4 additional kits after the birth. Each test will be accompanied with an
377 instruction sheet that describes step-by-step self-testing procedures in multiple languages. Study
378 staff will also provide participants with a brief demonstration of how to use the tests. Participants will
379 be encouraged to offer a test kit to their male partner or to use both test kits to undertake couples
380 testing if they feel comfortable doing so. They will also be counseled on how to talk to their partners
381 and the possibility of adverse partner reactions. Following Kenya's HIV testing services guidelines,
382 participants will be instructed to seek clinic-based confirmatory testing if a reactive self-test result is
383 obtained, and an invitation for confirmatory testing at a clinic will be included with each test. The
384 procedures used in the HIVST group are adapted from our experience developing and testing this
385 intervention in Kenya and have been found to be feasible and safe.[76, 77]

386 **Standard care:** All women in standard care are encouraged to come to the clinic with their male
387 partner and are encouraged to undergo CHTC. Clinic staff give women who attend alone a referral
388 letter to invite the male partner to ANC at the next visit. When couples come together to ANC, they
389 are given priority in the line to receive services. Despite these measures, our site assessments for
390 the current study indicate that less than 25% of pregnant women currently participate in couples
391 testing during ANC visits.

392 **Rationale for the comparison groups:** The HIVST and Standard Care arms are lower-cost by
393 design, since they do not include extensive health-related counseling and home visits. It is important
394 to compare our home-based couples intervention with these approaches for both efficacy and cost-
395 effectiveness, since male invitation letters are the current standard and HIVST has shown promise

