655 compared to the alternative strategies. However, cost-effectiveness might be sensitive to the intensity
656 of services provided, levels of compensation, extent of training, levels of adherence to ART treatment,
657 and other attributes. We will develop a decision analysis model using Tree Age Pro 2017 software
658 (Williamstown, MA, USA). We will use data on costs, changes in HIV status, and mortality to provide
659 inputs into a modified Markov model allowing for both transitions between health states and the
660 occurrence of transient adverse health outcomes. Markov models are among the most frequently used
661 modeling techniques in clinical decision analysis and health-economic evaluation, and are particularly
662 helpful when a decision analysis involves the analysis of risk over long periods of time.[167, 168] The
663 modification we propose will be a state transition model. State transition models combine Markov health
664 state transitions with the probability that individual will experience transient events that lead to either a
665 different health state (e.g. HIV transmission) or that can carry significant costs or mortality risk, such as
666 hospitalization for an opportunistic infection. State-transition models have been utilized in many
667 different populations and diseases, including diabetes, cardiovascular disease, HIV and malaria.[169-
668 171]

669 The final integrated decision model will consist of two parts. In the first part, a couple consisting of a
670 pregnant woman in antenatal care and her male partner, will be assigned to an arm of the decision
671 model (couple home visits, HIV self-test kits, standard of care). The probabilities of health state
672 transitions (e.g. changes in HIV status, viral load suppression, death) and adverse events will differ
673 based on the assigned arm of the decision model. Each woman and male partner enters the model as
674 HIV-negative or HIV-positive. Once a participant enters a new health state (HIV transmission), they
675 remain in that health state until suffering a next event (HIV transmission of a partner or death). In the
676 second part of the model, infant's transition states are considered (HIV-positive, HIV-negative, died).
677 These two parts will then be integrated into one overall model.

[figure not shown]
678 **Cost-effectiveness analytical plan:** In our analysis, we will follow The WHO Guide to Cost-

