679 Effectiveness Analysis for the conduct of CEA that is most applicable to developing countries.[172] To
680 determine the cost-effectiveness of the intervention, we will calculate **incremental cost-effectiveness
681 ratios (ICERs)** for the intervention versus each comparator (standard of care; distribution of HIV self-
682 test kits). The numerator of the ratio is the difference in costs expressed in US (purchasing parity
683 adjusted) Dollars; the denominator is the difference in effectiveness.[172, 173] A 10-year time horizon

684 will be used because an extrapolation beyond this would be associated with substantial increases in
685 uncertainty as to future developments in HIV prevention and treatment, as well as the lasting
686 effectiveness of the intervention. ICERs will be compared to the gross domestic product (GDP) as per
687 WHO recommendations to derive the following three categories of cost-effectiveness: highly cost-
688 effective (less than GDP per capita), cost-effective (between one and three times GDP per capita), and
689 not cost-effective (more than three times GDP per capita).

690 Following WHO Guide[172, 174], **the effectiveness** of the intervention will be assessed using the
691 Disability Adjusted Life Year (DALY) as the unit of effectiveness. One DALY represents a year of
692 healthy life lost due to death or disability.[175] We will calculate the DALY as the sum of the years of life
693 lost (YLL) and the years lost due to disability (YLD) that would be saved for each HIV infection averted
694 by study arm based on estimates and disability weights from the Global Burden of Disease (GBD).[176] We
695 will calculate the direct **costs** of each strategy utilizing established guidelines for costing HIV
696 interventions[177, 178] from a program perspective using micro-cost techniques. Cost estimation will
697 involve a uniform cost data collection protocol at each study site. We will conduct observations and
698 interviews with purposively selected sample of health care providers, study and assistant study
699 coordinators, finance and administration officers, to identify program activities on which resources were
700 spent. Expenditures will be classified in one of four categories; (i) personnel (including fringe benefits);
701 (ii) recurring supplies and services; (iii) durable equipment; and (iv) facility space. The costs of the

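### The GDP cut-offs for the ICERs carry no sign or dominance rule, so a home-visit arm dominated by self-test kits can read as highly cost-effective; kits against standard care is not listed

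*Combined protocol and SAP*

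**What the plan says.** Aim 3, under Study Aims, is "To compare the cost-effectiveness of the home-based couples intervention to less resource"-intensive strategies, namely standard care and self-test kits. The cost-effectiveness analytical plan calculates ICERs "for the intervention versus each comparator (standard of care; distribution of HIV self" (continuing to test kits). That gives two ratios: home visits against standard care, and home visits against kits. The ratio is a cost difference over an effect difference ("adjusted) Dollars; the denominator is the difference in effectiveness.[172, 173] A 10-year time horizon"), with DALYs as the unit of effect.

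The decision rule follows: "ICERs will be compared to the gross domestic product (GDP) as per" the WHO recommendations. The classes are highly cost-"effective (less than GDP per capita), cost-effective (between one and three times GDP per capita), and" "not cost-effective (more than three times GDP per capita").

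Three other places bear on the point.

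- The decision model covers every arm: "model (couple home visits, HIV self-test kits, standard of care). The probabilities of health state" transitions then differ by arm. Costs are collected for each strategy.
- The rationale for the comparison groups says "The HIVST and Standard Care arms are lower-cost by" design, so home visits are expected to be the costliest to deliver.
- The power section makes all three pairwise comparisons for couple testing, and Expected Application of Results promises comparative evidence on all three approaches.

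The economic sections contain no ranking of strategies, dominance step, treatment of negative ratios, or net-benefit measure. They do not say which label governs if the two ICERs disagree, or how the probabilistic simulations will be summarised.

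**The concern.** The three arms are mutually exclusive options. A ratio has a clear meaning against a cut-off only when the option costs more and achieves more than the one it is compared with. A negative ratio can mean cheaper and better, or dearer and worse. A rule that reads only the value cannot tell these apart, and it places both below one GDP per capita.

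The case is not far-fetched. If home visits cost most, dominance by kits turns only on the sign of the home-minus-kits effect. Table 2 uses one shared range of uptake for either intervention arm. The human-subjects section also reports an earlier kit trial with couples testing of 75.4% against 33.2%. Uptake is not DALYs, but nothing in these figures makes a small or negative home-minus-kits effect implausible.

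At stake is the Aim 3 conclusion given to policymakers. A home-visit arm that kits beat on both cost and effect could be reported with two favourable labels.

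**Working it through.** The plan states no ICER, cost, DALY or GDP value, so there is no figure to reproduce. The check applies the written rule to assumed inputs.

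**Assumptions.** GDP per capita = 1. Standard care = (cost 0, DALYs averted 0). Costs of the other arms are in GDP units and effects in DALYs averted, both relative to standard care.

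**Rule.** ICER = cost difference / difference in DALYs averted. Below 1 is highly cost-effective, 1 to 3 cost-effective, above 3 not cost-effective.

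| Case | Kits (cost, effect) | Home (cost, effect) | Home vs standard | Home vs kits | Kits vs standard (not listed) |
|---|---|---|---|---|---|
| A: home dominated by kits | 0.5, 1.0 | 1.5, 0.9 | 1.5/0.9 = 1.67, cost-effective | (1.5-0.5)/(0.9-1.0) = -10, highly cost-effective if read literally | 0.5/1.0 = 0.50 |
| B: home slightly better than kits | 0.5, 1.0 | 1.5, 1.05 | 1.5/1.05 = 1.43, cost-effective | (1.5-0.5)/(1.05-1.0) = 20, not cost-effective | 0.5/1.0 = 0.50 |
| C: kits extendedly dominated | 0.5, 0.1 | 1.5, 1.0 | 1.5/1.0 = 1.50, cost-effective | (1.5-0.5)/(1.0-0.1) = 1.11, cost-effective | 0.5/0.1 = 5.0 |

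**Case A.** Both planned ratios are favourable for a strategy that should be removed. A home-visit arm that saved 1.0 and averted 0.1 more DALYs than kits would also give -1.0/0.1 = -10, the same value with the opposite meaning.

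**Case B.** The labels differ and the plan does not say which stands.

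**Case C.** Kits are the poor-value option (5.0), so the relevant ratio for home visits is 1.50 against standard care. The planned ratio against kits, 1.11, flatters them, though the label is the same.

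**Range for dominated home visits.** Hold kits at (0.5, 1.0) and vary home visits over cost 0.75 to 3.5 and effect 0.5 to 0.9. Home vs standard care runs from 0.75/0.9 = 0.83 to 3.5/0.5 = 7.0, so that label depends on the inputs. Home vs kits runs from (0.75-0.5)/(0.5-1.0) = -0.5 to (3.5-0.5)/(0.9-1.0) = -30. It is negative throughout, so the literal label is highly cost-effective throughout.

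**Full incremental analysis of the same inputs.**

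- A: home visits removed; kits vs standard care 0.50.
- B: standard care, then kits (0.50), then home visits (20, not cost-effective).
- C: kits removed; home visits vs standard care 1.50.

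**Net benefit** (threshold x effect - cost; standard care = 0), case A. At one GDP, kits 1.0-0.5 = 0.5 and home visits 0.9-1.5 = -0.6. At three GDP, kits 3.0-0.5 = 2.5 and home visits 2.7-1.5 = 1.2. Kits rank first at both thresholds, and no sign problem arises.

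**The case against.** Much can be said for the plan, and several stronger readings that a reader might infer are not supported.

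- *That Aim 3 asks which of three strategies is best value.* It does not. It is framed around home visits against two cheaper strategies, and the two planned ICERs match that wording. Leaving out kits against standard care is a limit of scope. It sits poorly with the three-way evidence promised under Expected Application of Results and with the three efficacy comparisons, but it does not contradict the aim.
- *That the decisive ratio is missing.* When kits are on the frontier, the ratio that matters for home visits is home against kits, and that one is planned.
- *That the plan cannot show whether kits are worth adopting.* Kits against standard care follows by subtraction. In case A the cost is 1.5-1.0 = 0.5, the effect is 0.9-(-0.1) = 1.0, and the ratio is 0.50. No information is lost; the ratio is simply not listed or judged.
- *That mislabelling will happen.* The analyst forms the numerator and denominator separately and would probably notice an arm that costs more and averts less. Aim 3 itself asks about value for money, which such an arm plainly fails to offer.
- *That no dominance rule governs the analysis.* The plan says it follows the WHO guide, whose content is not in the documents. One can say only that the protocol does not restate such a rule.

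What remains is that the one decision rule written down is a rule on the value of the ratio. It gives the wrong class to a negative ratio from a dominated arm and no answer when the labels differ.

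**Conclusion.** The concern holds as a gap in the written decision rule. Applied literally, the rule places home visits in the most favourable class against kits whenever they cost more and avert fewer DALYs, and it may also class them as cost-effective against standard care. Probabilistic draws would be affected in the same way if they are scored by ICER value, which the plan leaves open.

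The size is illustrative only. The labels rest on assumed costs and effects, on the expectation that home visits cost most, and on a literal reading of the cut-offs. If home visits turn out both the costliest and the most effective, they cannot be dominated. The remaining problem is then a high ICER against kits beside an acceptable one against standard care, with no rule for which governs.

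The point affects what Aim 3 can conclude. It does not touch randomization, data collection, power, or the analyses for Aims 1 and 2. It should be corrected before the economic analysis is run.

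**What to change.** In the cost-effectiveness analytical plan, pre-specify a full incremental analysis of the three arms:

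1. Rank standard care, kits and home visits by mean cost.
2. Remove any strategy that is dominated (costs at least as much and averts no more DALYs, with at least one of these strictly worse) or extendedly dominated.
3. Report sequential ICERs for the strategies that remain, including kits against standard care when both are on the frontier.
4. Apply the GDP cut-offs only to those ICERs. Report removed strategies as dominated, without a ratio.
5. Summarise the probabilistic runs already planned by net benefit per arm at the stated thresholds, not by counting ICERs below a cut-off.

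The two pairwise contrasts in Aim 3 can still be shown, as cost and effect differences with their signs.

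The cost is a few sentences and minor extra analysis. All three arms are already modelled and costed, so no new data are needed. The possible downside for the investigators is a less favourable label for home visits.

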702 program will be identified through interviews with administrative, finance and human resources officers,
703 supplemented by direct observation in a limited number of formal “time and motion” studies. Costs for
704 equipment and facility space (likely a small portion of total costs) will be amortized on a straight-line
705 basis over their expected useful life assuming no salvage value. Other costs considered include
706 laboratory, medication, and healthcare costs. We will account for costs related to increased use of
707 PrEP, HIV or pregnancy-related services. Research costs (e.g. costs related to consenting and
708 research-participation), any medical costs incurred offsite, or higher-level program costs incurred by the
709 county/national government or donors will be excluded from the programmatic costs. Costs and DALYs
710 will be discounted at a 3% rate.[172]

711 A key element of cost-effectiveness analysis involves properly accounting for the uncertainty
712 associated with the ICER. Such ratios are estimates based on a sample of individuals. They are subject
713 to sampling error, and performing the same trial over and over would lead to different estimates of the
714 ratio. A variety of **sensitivity analyses** will be used to assess the performance of our state transition
715 models.[172] One-way sensitivity analyses will be used to determine which model parameters are most
716 important in determining whether the intervention can be considered cost-effective. Some anticipated
717 parameters include certain clinical practice situations such as decreased testing, initiation, adherence
718 and retention into care, and varying costs of inputs, particularly for the antiretrovirals. Markov Chain
719 Monte Carlo probabilistic sensitivity analyses simulations will then be used to test the robustness of the
720 model findings to uncertainty in the parameter inputs.

721 722 TIME FRAME

723
724
725

726 Aim 1 of this study is to determine the impact of a couples-focused home-based intervention on our
727 primary outcome of couple HIV testing for pregnant women and their male partners as compared to
728 HIV self-test kits for couples and standard care. There is a need to understand how COVID-19 has
729 influenced the Jamii Bora study, participating health facilities, and the study participants. There is also a
730 lack of data on how the new coronavirus has affected research teams and studies, both in their

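### As written, DALYs are credited per HIV infection averted, while costs include added HIV and pregnancy care and the model tracks suppression and death; taken literally, the ICER leaves out part of the health gain

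*Combined protocol and SAP*

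**What the plan says.** The cost-effectiveness analytical plan takes the "Disability Adjusted Life Year (DALY) as the unit of effectiveness". It then gives its one rule for computing it: the sum of years of life "lost (YLL) and the years lost due to disability (YLD) that would be saved for each HIV infection averted", by arm, using Global Burden of Disease weights. The ICER is a cost difference in "adjusted) Dollars; the denominator is the difference in effectiveness.[172, 173] A 10-year time horizon" applies, and costs and DALYs "will be discounted at a 3% rate.[172".

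On the cost side the same section lists "laboratory, medication, and healthcare costs. We will account for costs related to increased use of" "PrEP, HIV or pregnancy-related services".

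The model under Cost-Effectiveness Analysis for Aim 3 is broader than the DALY rule. On its inputs it says "We will use data on costs, changes in HIV status, and mortality to provide" them. For women and men, the probabilities of health state "transitions (e.g. changes in HIV status, viral load suppression, death) and adverse events will differ" by arm. It allows transient events that carry mortality risk, and the infant part has a died state.

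**The concern.** The numerator and denominator of an ICER should cover the same consequences. Here the costs follow all added HIV and pregnancy care, while the written effectiveness rule follows one route to health, the infection averted.

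This matters in this population. By design 533 of the 800 women are HIV-positive at baseline, and no infection can be averted in them. Under the written rule their treatment counts only through infections prevented in partners and infants. A man found to be HIV-positive and started on ART likewise earns nothing for his own health. Yet new male diagnoses (Aim 1) and facility delivery, postnatal care, maternal suppression and HIV-free child survival (Aim 2) are outcomes the trial sets out to change.

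An arm that links more people to care would have its costs rise in full and its benefit rise only in part. The ICER is then sorted into categories at one and three times GDP per capita. The planned one-way and probabilistic sensitivity analyses vary parameter values and do not change what the denominator counts, so they would not expose the problem.

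**Working it through.** The documents state no ICER, DALY total, cost total or GDP value, so there is no figure to reproduce. The main check is a comparison of texts. The arithmetic after it is illustration only.

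**1. Costs, DALY rule and model side by side**

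| Benefit | Can add cost in the numerator? | DALY under the written rule? | In the Aim 3 model? |
|---|---|---|---|
| Partner infection averted through PrEP | Yes, PrEP | Yes | Yes, HIV status |
| Partner or infant infection averted through ART | Yes, HIV services | Yes | Yes, HIV status; infant HIV states |
| Newly diagnosed man: own morbidity and survival | Yes, HIV services | No | Yes, suppression and death |
| HIV-positive woman newly suppressed: own health | Yes, so far as HIV service use rises | No | Yes, suppression and death |
| Non-HIV maternal or infant death avoided | Yes, pregnancy-related services | No | Yes, death; infant died state |

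The last three rows are the gap. No sentence says how those modelled states and deaths become YLL or YLD.

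**2. Discount factor.** With the plan's 10 years and 3%: (1 − 1.03^−10)/0.03 = (1 − 0.7441)/0.03 = 8.53. Continuous discounting gives 8.64. One adult death averted at the start therefore carries about 8.5 discounted years within the horizon. The written rule does not credit them unless an infection was averted.

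**3. Women, using the plan's own scenario**
- Inputs: 178 HIV-positive women per arm (Study design); suppression of 85% against 95% (Sample size and power calculations).
- Extra women suppressed: 178 × (0.95 − 0.85) = 17.8.
- Assumed disability-weight gain of 0.05 to 0.30, held for 10 years (neither assumption is in the documents).
- Uncredited discounted YLD: 17.8 × 0.05 × 8.53 = 7.6, up to 17.8 × 0.30 × 8.53 = 45.6 per arm.

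**4. Newly diagnosed men, all inputs assumed except horizon and discount rate.** With 2 to 5 extra men on ART per 100 couples and a gain of 0.1 to 0.2 DALY a year for 10 years: 2 × 0.1 × 8.53 = 1.7, up to 5 × 0.2 × 8.53 = 8.5 uncredited DALYs per 100 couples.

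**5. Effect on the ICER.** Let D_I be DALYs averted through infections averted, D_T the other DALYs averted, ΔC the cost difference, and R = D_T/D_I. With ΔC, D_I and D_T all positive:

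ICER(written) / ICER(full) = (ΔC/D_I) / (ΔC/(D_I + D_T)) = 1 + R.

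| R (assumed) | Overstatement of ICER | Written-rule ICERs above 3 × GDP whose full ICER is at or below 3 × GDP |
|---|---|---|
| 0.25 | ×1.25 | 3 to 3.75 × GDP |
| 0.5 | ×1.5 | 3 to 4.5 × GDP |
| 1 | ×2 | 3 to 6 × GDP |

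Nothing in the documents fixes R, because D_I is unknown as well as D_T. The totals in steps 3 and 4 cannot be turned into a share of the denominator.

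**The case against.** The strongest reply is that the rule is one loosely worded sentence. It does not use the word only. The sentence before it defines a DALY generally, as healthy life lost through death or disability. The model has suppression, death and an infant died state, so it could produce every YLL and YLD in question, and the analysts may intend to use them. A figure near the model description is also missing from the text available here and may show payoffs by state. All of that is fair, and it is why the point is limited to the plan as written. It does not remove the point: the one computational rule given is tied to infections averted, and nothing else links the model's other outputs to the denominator.

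Second, much of the charged care does earn credit. PrEP works by averting infection. Couples known to be concordant positive are excluded, so ART can earn credit through partners as well as infants. This stands, and it narrows the gap to the last three rows of the table.

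Third, under Option B+ (The setting) all HIV-positive pregnant and breastfeeding women start lifelong ART, so maternal ART cost is largely common to the arms. Costs are also from a program perspective and exclude offsite medical costs and those borne by government or donors. This stands too. It weakens the mismatch for women, and the plan does not say that ten years of ART is charged for each newly diagnosed man. It does not restore the missing health gain.

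Fourth, the bias would be conservative, since it works against the home-visit arm that the investigators expect to be cost-effective. That holds only if home visits raise linkage most. In any case an understated benefit can mislead an adoption decision as much as an overstated one.

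**Conclusion.** The point holds for the plan as written. The DALY rule, the cost scope and the model do not match. Followed literally, the rule drops the own-health gain of people already HIV-positive and non-HIV maternal or infant deaths avoided, and so biases the ICER against whichever arm increases linkage to care. It concerns Aim 3 only; the couple-testing analysis is untouched. It should be settled before results are known, because the choice of denominator could otherwise be made with the ICER in view.

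The size is unknown. The DALY totals rest on assumed disability weights, assumed numbers of men and full persistence over 10 years. The 1 + R relation is exact for the stated signs, but R is assumed.

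A reader might infer that the ICER charges for treatment and credits none of its health gain, or that the cost-effectiveness category will change. The documents support neither. Part of the gain is credited through infections averted, the model could supply the rest, and without an ICER, a DALY total or a GDP value no change of category can be shown.

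**What to change.** Replace the DALY rule in the cost-effectiveness analytical plan with wording such as:

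> DALYs averted are the difference between arms in discounted YLL and YLD accumulated over the 10-year horizon by the woman, the man and the infant. They are computed from time in each modelled state (HIV-negative, HIV-positive suppressed, HIV-positive unsuppressed) and from all modelled deaths. DALYs due to HIV infections averted will be reported as one component of this total.

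The component is a breakdown of the total and must not be added to it, since infections averted already change state occupancy. If the model figure shows payoffs by state, the text should refer to it.

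The cost is small: a changed output definition, some extra modelling work, and disability weights by treatment state. Suppression and death transitions for the adults and a died state for the infant are already planned, and no new trial data are needed.
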